6.3.3 Response Criteria for ATLL

Table 12: Response Criteria for Adult T-cell Leukemia-Lymphoma

Response	Definition	Lymph nodes	Extranodal masses	Spleen, liver	Skin	Peripheral blood	Bone marrow
CR*	Disappearance of all disease	Normal	Normal	Normal	Normal	Normal †	Normal
CRu*	Stable residual mass in bulky lesion	$\geq 75\%$ decrease ‡	$\geq 75\%$ decrease ‡	Normal	Normal	Normal †	Normal
PR*	Regression of disease	$\geq 50\%$ decrease ‡	$\geq 50\%$ decrease ‡	No increase	$\geq 50\%$ decrease	$\geq 50\%$ decrease	Irrelevant
SD*	Failure to attain CR/PR and no PD	No change in size	No change in size	No change in size	No change in size	No change	No change

Abbreviated Title: IL-15+Mogamulizumab

Version Date: 11/16/2020

RD/PD	New or increased lesions	New or $\geq 50\%$ increase §	New or $\geq 50\%$ increase §	New or $\geq 50\%$ increase	$\geq 50\%$ increase	New or $\geq 50\%$ increase	Reappearance
Not assessable							
CR: complete response, CRu: unconfirmed complete response, PR: partial response, SD: stable disease, RD/PD: relapsed disease/progressive disease *Require each criterion to be present for a period of at least 4 weeks. † Provided that $<5\%$ of flower cells remained, complete remission will be judged to have been attained if the absolute lymphocyte count, including flower cells is $< 4 \times 10^9/L$. ‡ Calculated by the sum of the products of the greatest diameters of measurable disease. § Defined by $\geq 50\%$ increase from nadir in the sum of the products of measurable disease. Defined by $\geq 50\%$ increase from nadir in the count of flower cells and an absolute lymphocyte count, including flower cells, of $> 4 \times 10^9/L$.							

6.3.4 Best Overall Response

The best overall response is the best response recorded from the start of the treatment until disease progression/recurrence (taking as reference for progressive disease the smallest measurements recorded since the treatment started).

6.3.5 Duration of Response

The duration of response (DOR) is measured from the time measurement criteria are met for CR or PR (whichever is recorded first) until the first date that recurrent or progressive disease is objectively documented (taking as reference for progressive disease the smallest measurements recorded since the treatment started), death, or, in the absence of PD, date of last assessment.

6.3.6 Progression-Free Survival

Progression-free survival (PFS) is defined as the duration of time from the date of study enrollment until time of disease relapse, disease progression, or death, whichever occurs first.

6.3.7 Overall Survival

Overall survival (OS) is defined as the time from the date of study enrollment until time of death from any cause.

6.3.8 Event-Free Survival

Event-free survival (EFS) is defined as the duration of time from the date of study enrollment until time of disease relapse, disease progression, alternative therapy for lymphoma given (such as radiation), or death, whichever occurs first.

6.3.9 Duration of Response

Duration of overall response: The duration of overall response is measured from the time measurement criteria are met for CR or PR (whichever is first recorded) until the first date that

Abbreviated Title: IL-15+Mogamulizumab

Version Date: 11/16/2020

recurrent or progressive disease is objectively documented (taking as reference for progressive disease the smallest measurements recorded since the treatment started).

The duration of overall CR is measured from the time measurement criteria are first met for CR until the first date that progressive disease is objectively documented.

Duration of stable disease: Stable disease is measured from the start of the treatment until the criteria for progression are met, taking as reference the smallest measurements recorded since the treatment started, including the baseline measurements.

6.4 TOXICITY CRITERIA

The following adverse event management guidelines are intended to ensure the safety of each patient while on the study. The descriptions and grading scales found in the revised NCI Common Terminology Criteria for Adverse Events (CTCAE) version 5.0 will be utilized for AE reporting. All appropriate treatment areas should have access to a copy of the CTCAE version 5.0. A copy of the CTCAE version 5.0 can be downloaded from the CTEP web site (http://ctep.cancer.gov/protocolDevelopment/electronic_applications/ctc.htm).

7 NIH REPORTING REQUIREMENTS / DATA AND SAFETY MONITORING PLAN

7.1 DEFINITIONS

Please refer to definitions provided in Policy 801: Reporting Research Events found [here](#).

7.2 OHSRP OFFICE OF COMPLIANCE AND TRAINING / IRB REPORTING

7.2.1 Expedited Reporting

Please refer to the reporting requirements in Policy 801: Reporting Research Events and Policy 802 Non-Compliance Human Subjects Research found [here](#). **Note:** Only IND Safety Reports that meet the definition of an unanticipated problem will need to be reported per these policies.

7.2.2 IRB Requirements for PI Reporting at Continuing Review

Please refer to the reporting requirements in Policy 801: Reporting Research Events found [here](#).

7.3 NCI CLINICAL DIRECTOR REPORTING

Problems expeditiously reported to the OHSRP in iRIS will also be reported to the NCI Clinical Director. A separate submission is not necessary as reports in iRIS will be available to the Clinical Director.

In addition to those reports, all deaths that occur within 30 days after receiving a research intervention should be reported via email to the Clinical Director unless they are due to progressive disease.

To report these deaths, please send an email describing the circumstances of the death to [name] at [contact] within one business day of learning of the death.

Abbreviated Title: IL-15+Mogamulizumab

Version Date: 11/16/2020

7.4 NIH REQUIRED DATA AND SAFETY MONITORING PLAN

7.4.1 Principal Investigator/Research Team

The clinical research team will meet at least once weekly when patients are being actively treated on the trial to discuss each patient. Decisions about dose level enrollment and dose escalation if applicable will be made based on the toxicity data from prior patients.

All data will be collected in a timely manner and reviewed by the principal investigator or a lead associate investigator. Events meeting requirements for expedited reporting as described in Section [7.2.1](#) will be submitted within the appropriate timelines.

The principal investigator will review adverse event and response data on each patient to ensure safety and data accuracy. The principal investigator will personally conduct or supervise the investigation and provide appropriate delegation of responsibilities to other members of the research staff.

8 SPONSOR SAFETY REPORTING

8.1 DEFINITIONS

8.1.1 Adverse Event

Any untoward medical occurrence in a patient or clinical investigation subject administered a pharmaceutical product and which does not necessarily have a causal relationship with this treatment. An adverse event (AE) can therefore be any unfavorable and unintended sign (including an abnormal laboratory finding), symptom, or disease temporally associated with the use of a medicinal (investigational) product, whether or not related to the medicinal (investigational) product (ICH E6 (R2))

8.1.2 Serious Adverse Event (SAE)

An adverse event or suspected adverse reaction is considered serious if in the view of the investigator or the sponsor, it results in any of the following:

- Death,
- A life-threatening adverse event (see [8.1.3](#))
- Inpatient hospitalization or prolongation of existing hospitalization
 - A hospitalization/admission that is pre-planned (i.e., elective or scheduled surgery arranged prior to the start of the study), a planned hospitalization for pre-existing condition, or a procedure required by the protocol, without a serious deterioration in health, is not considered a serious adverse event.
 - A hospitalization/admission that is solely driven by non-medical reasons (e.g., hospitalization for patient convenience) is not considered a serious adverse event.
 - Emergency room visits or stays in observation units that do not result in admission to the hospital would not be considered a serious adverse event. The reason for seeking medical care should be evaluated for meeting one of the other serious criteria.
- Persistent or significant incapacity or substantial disruption of the ability to conduct normal life functions

Abbreviated Title: IL-15+Mogamulizumab

Version Date: 11/16/2020

- A congenital anomaly/birth defect.
- Important medical events that may not result in death, be life-threatening, or require hospitalization may be considered a serious adverse drug experience when, based upon appropriate medical judgment, they may jeopardize the patient or subject and may require medical or surgical intervention to prevent one of the outcomes listed in this definition.

8.1.3 Life-threatening

An adverse event or suspected adverse reaction is considered “life-threatening” if, in the view of either the investigator or sponsor, its occurrence places the patient or subject at immediate risk of death. It does not include an adverse event or suspected adverse reaction that, had it occurred in a more severe form, might have caused death (21CFR312.32)

8.1.4 Severity

The severity of each Adverse Event will be assessed utilizing the CTCAE version 5.

8.1.5 Relationship to Study Product

All AEs will have their relationship to study product assessed using the terms: related or not related.

- Related – There is a reasonable possibility that the study product caused the adverse event. Reasonable possibility means that there is evidence to suggest a causal relationship between the study product and the adverse event.
- Not Related – There is not a reasonable possibility that the administration of the study product caused the event.

8.2 ASSESSMENT OF SAFETY EVENTS

AE information collected will include event description, date of onset, assessment of severity and relationship to study product and alternate etiology (if not related to study product), date of resolution of the event, seriousness and outcome. The assessment of severity and relationship to the study product will be done only by those with the training and authority to make a diagnosis and listed on the Form FDA 1572 as the site principal investigator or sub-investigator. AEs occurring during the collection and reporting period will be documented appropriately regardless of relationship. AEs will be followed through resolution.

SAEs will be:

- Assessed for severity and relationship to study product and alternate etiology (if not related to study product) by a licensed study physician listed on the Form FDA 1572 as the site principal investigator or sub-investigator.
- Recorded on the appropriate SAE report form, the medical record and captured in the clinical database.
- Followed through resolution by a licensed study physician listed on the Form FDA 1572 as the site principal investigator or sub-investigator.

Abbreviated Title: IL-15+Mogamulizumab

Version Date: 11/16/2020

For timeframe of recording adverse events, please refer to Section **6.1**. All serious adverse events recorded from the time of first investigational product administration recorded must be reported to the sponsor with the exception of any listed in section **8.4**.

8.3 REPORTING OF SERIOUS ADVERSE EVENTS

Any AE that meets protocol-defined serious criteria or meets the definition of Adverse Event of Special Interest that require expedited reporting must be submitted immediately (within 24 hours of awareness) to OSRO Safety using the CCR SAE report form. Any exceptions to the expedited reporting requirements are found in section **8.4**.

All SAE reporting must include the elements described in section **8.2**.

SAE reports will be submitted to the Center for Cancer Research (CCR) at:

[contact] and to the CCR PI and study coordinator. CCR SAE report form and instructions can be found at:

<https://ccrod.cancer.gov/confluence/pages/viewpage.action?pageId=157942842>

Following the assessment of the SAE by OSRO, other supporting documentation of the event may be requested by the OSRO Safety and should be provided as soon as possible.

8.4 WAIVER OF EXPEDITED REPORTING TO CCR

As death due to disease progression is part of the study objectives, and captured as an endpoint in this study, it will not be reported in expedited manner to the sponsor. However, if there is evidence suggesting a causal relationship between the study drug and the event, report the event in an expedited manner according to section **8.3**.

8.5 SAFETY REPORTING CRITERIA TO THE PHARMACEUTICAL COLLABORATORS

Reporting will be per the collaborative agreement.

8.5.1 CTEP

Copies of all IND Safety Reports submitted to the FDA should be forwarded electronically to [contact] (please provide protocol number in subject line).

8.6 REPORTING PREGNANCY

8.6.1 Maternal exposure

If a patient becomes pregnant during the course of the study, the study treatment should be discontinued immediately, and the pregnancy reported to the Sponsor no later than 24 hours of when the Investigator becomes aware of it. The Investigator should notify the Sponsor no later than 24 hours of when the outcome of the Pregnancy becomes known,

Pregnancy itself is not regarded as an SAE. However, congenital abnormalities or birth defects and spontaneous miscarriages that meet serious criteria section **8.1.2**) should be reported as SAEs.

The outcome of all pregnancies (spontaneous miscarriage, elective termination, ectopic pregnancy, normal birth, or congenital abnormality) should be followed up and documented.

Abbreviated Title: IL-15+Mogamulizumab

Version Date: 11/16/2020

8.6.2 Paternal exposure

Male patients should refrain from fathering a child or donating sperm during the study and for 6 months after the last dose of mogamulizumab.

Pregnancy of the patient's partner is not considered to be an AE. However, the outcome of all pregnancies (spontaneous miscarriage, elective termination, ectopic pregnancy, normal birth, or congenital abnormality) occurring from the date of the first dose until 90 days after the last dose should, if possible, be followed up and documented.

8.7 REGULATORY REPORTING FOR STUDIES CONDUCTED UNDER CCR-SPONSORED IND

Following notification from the investigator, CCR, the IND sponsor, will report any suspected adverse reaction that is both serious and unexpected. CCR will report an AE as a suspected adverse reaction only if there is evidence to suggest a causal relationship between the study product and the adverse event. CCR will notify FDA and all participating investigators (i.e., all investigators to whom the sponsor is providing drug under its INDs or under any investigator's IND) in an IND safety report of potential serious risks from clinical trials or any other source, as soon as possible, in accordance to 21 CFR Part 312.32.

All serious events will be reported to the FDA at least annually in a summary format.

9 CLINICAL MONITORING

As a sponsor for clinical trials, FDA regulations require the CCR to maintain a monitoring program. The CCR's program allows for confirmation of: study data, specifically data that could affect the interpretation of primary and secondary study endpoints; adherence to the protocol, regulations, ICH E6, and SOPs; and human subjects protection. This is done through independent verification of study data with source documentation focusing on:

- Informed consent process
- Eligibility confirmation
- Drug administration and accountability
- Adverse events monitoring
- Response assessment.

The monitoring program also extends to multi-site research when the CCR is the coordinating center.

This trial will be monitored by personnel employed by a CCR contractor. Monitors are qualified by training and experience to monitor the progress of clinical trials. Personnel monitoring this study will not be affiliated in any way with the trial conduct.

10 STATISTICAL CONSIDERATIONS

10.1 STATISTICAL HYPOTHESIS

- Primary Endpoint(s):
 - Maximum tolerated dose (MTD) of rhIL-15 administered intravenously for 5 days in combination with mogamulizumab for up to 6 cycles
 - Frequency (number and percentage) of treatment-emergent AEs
- Secondary Endpoint(s):
 - Overall response rate (including CR and PR)

Abbreviated Title: IL-15+Mogamulizumab

Version Date: 11/16/2020

- ORR, TTP, and PFS by CCR4 mutation status (mutated versus wild type) and presenting diagnosis (MF/SS versus ATLL, MF versus SS, acute/chronic versus lymphoma subtype ATLL)
- Duration of response
- Progression-free, event-free, and overall survival
- Changes in percentage and absolute number of peripheral blood lymphocyte subsets
- Quantitation ADCC performed ex vivo on PBMCs obtained from the patients before and during treatment
- Characterization of changes in immune cell infiltrates of tumor deposits by immunohistochemical and molecular analysis of core biopsies obtained before and during treatment

10.2 SAMPLE SIZE DETERMINATION

The MTD will be based on the assessment of DLT during the first cycle of treatment and will be defined as the dose level at which less than one-third of patients (0 of 3 or 0-1/6 patients) treated experience a DLT, with the next higher dose level demonstrating one-third or a greater number of patients (≥ 2 -3 or ≥ 2 -6 patients) having a DLT. If a subject did not experience a DLT and did not finish one cycle of treatment (28 days) he or she will not be evaluable for determination of the MTD and would be replaced in the dose level. An additional 6 to 9 patients will be enrolled at the MTD, so that a total of 12 patients will be treated at this dose.

Using this dose-escalation scheme the probability of escalating to the next dose level will be based on the true rate of DLT at the current doses given by the following table (each group will be considered independently of the other); Thus, if the true underlying proportion of DLTs is 50% at the current dose there is a 17% probability of escalating to the next dose.

True toxicity at a given dose	10%	20%	30%	40%	50%	60%
Probability of escalating	0.91	0.71	0.49	0.31	0.17	0.08

If both dose levels are evaluated with 6 patients per dose level and 12 total patients at the MTD, a maximum of 18 evaluable patients will be enrolled. Similarly, if all dose levels are evaluated with 3 patients per dose level and 12 total patients at the MTD, the minimum number of evaluable patients required will be 15. To account of unevaluable patients, accrual ceiling will be set at 20. It is expected that the accrual can be completed in 18 months.

A maximum of 18 patients will be enrolled over 18 months, at a rate of 1 patient per month.

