2.3.2.2 Arms

Number	Name	Description
1	Experimental Treatment: Dose Escalation	IL-15 by CIV infusion at escalating doses of 2 and 4 mcg/kg/day on days 1-5 of each 28-day cycle (max 6 cycles) with mogamulizumab by IV infusion at a dose of 1 mg/kg on days 1, 8, 15, and 22 of cycle 1 and days 1 and 15 of cycles 2-6, to determine MTD

Abbreviated Title: IL-15+Mogamulizumab

Version Date: 11/16/2020

Number	Name	Description
2	Experimental Treatment: Dose Expansion	IL-15 by CIV infusion at the MTD on days 1-5 of cycles 1-6 with mogamulizumab at 1 mg/kg on days 1, 8, 15, and 22 of cycle 1 and days 1 and 15 of cycles 2-6

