3.1 STUDY DESIGN

In patients with relapsed/refractory MF/SS or ATLL, IL-15 will be administered by continuous intravenous infusion in a dose-escalation 3 + 3 system with a starting dose of 2 mcg/kg/day and a second dose level of 4 mcg/kg/day on days 1-5 of each of six cycles. Mogamulizumab will be

Abbreviated Title: IL-15+Mogamulizumab

Version Date: 11/16/2020

administered IV over at least 1 hour at a dose of 1 mg/kg on days 1, 8, 15 and 22 of cycle 1, and days 1 and 15 of each subsequent cycle. Treatment will continue for a maximum of 6 cycles or until toxicity (i.e., dose limiting toxicity as found in Section 3.1.1 or toxicity requiring hold as defined in Section 3.3) or progressive disease.

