3.1.2 Dose Escalation

Dose escalation will proceed according to the following schedule (**Table 6**). Dose escalation will follow the following guidelines (**Table 7**). DLT is defined above. Each patient will continue treatment at the dose level they were enrolled – there will be no intra-patient dose escalation.

The MTD is the dose level at which no more than 1 of up to 6 patients experience DLT during the DLT evaluation window(s), or the dose below that at which at least 2 (of ≤ 6) patients have DLT. The protocol will be amended to note the MTD once determined.

Table 6: IL-15 Dose Escalation Schedule

Dose Level	rhIL-15 (mcg/kg)	Mogamulizumab (mg/kg)
Level 1	2	1
Level 2	4	1

*Doses are stated as exact dose in units (e.g., mg/m², mcg/kg, etc.) rather than as a percentage.

Table 7: Dose Escalation Guidelines

Number of Patients with DLT at a Given Dose Level	Escalation Decision Rule
0 out of 3	Enter 3 patients at the next dose level.
≥ 2	Dose escalation will be stopped. This dose level will be declared the maximally administered dose (highest dose administered). Three (3) additional patients will be entered at the next lowest dose level if only 3 patients were treated previously at that dose.
1 out of 3	Enter at least 3 more patients at this dose level. 
 • If 0 of these 3 patients experience DLT, proceed to the next dose level. • If 1 or more of this group suffer DLT, then dose escalation is stopped, and this dose is declared the maximally administered dose. Three (3) additional patients will be entered at the next lowest dose level if only 3 patients were treated previously at that dose.
≤ 1 out of 6 at highest dose level below the maximally administered dose	This is generally the recommended phase 2 dose. At least 6 patients must be entered at the recommended phase 2 dose.

Abbreviated Title: IL-15+Mogamulizumab

Version Date: 11/16/2020

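### The MTD definitions in 10.2 and 3.1.2 disagree about the top dose: 10.2 can never name 4 mcg/kg/day and returns no MTD if both levels are tolerated

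*Combined protocol and SAP*

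**What the plan says.** Section 3.1 sets two levels of rhIL-15, "a starting dose of 2 mcg/kg/day and a second dose level of 4 mcg/kg/day", and Table 6 and the description of Arm 1 in 2.3.2.2 list the same two. The MTD is one of two primary endpoints in 10.1: "Maximum tolerated dose (MTD) of rhIL-15 administered intravenously for 5 days in combination with mogamulizumab for up to 6 cycles". The other is the frequency of treatment-emergent adverse events. The MTD also sets the expansion dose, because Arm 2 receives "IL-15 by CIV infusion at the MTD on days 1-5 of cycles 1-6" and no dose in mcg/kg is given.

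The MTD is defined twice.

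- **Section 10.2** joins two conditions. The level must have 0/3 or at most 1/6 DLTs, "with the next higher dose level demonstrating one-third or a greater number of patients" having a DLT.
- **Section 3.1.2** offers two alternatives: "The MTD is the dose level at which no more than 1 of up to 6 patients experience DLT" in the evaluation window, "or the dose below that at which at least 2" patients have a DLT.

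Table 7 gives the escalation decisions. After 0/3, three patients enter at the next level. After 1/3, three more are treated at the same level: "If 0 of these 3 patients experience DLT, proceed to the next dose level". Its last row identifies the usual recommended phase 2 dose as the highest level below the maximally administered dose, with at most 1/6 DLTs.

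**The concern.** A definition that needs a failing higher level works only where a higher level exists. With two levels, 10.2 can return level 1 or nothing. The result it cannot return is the one an escalation hopes for: both doses tolerated, and the higher one taken forward.

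At stake are a primary endpoint and the dose given to the expansion patients, up to nine according to 2.3.2.1. Two sections define the endpoint differently. If both levels clear, one names no dose and the other can be met by more than one. Section 3.1.2 says that the protocol will be amended to note the MTD once determined, but that records a result and supplies no rule for reaching it. The rule should be fixed before the DLT data are seen.

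**Working it through.** **1. Reproduce the plan's table.** Let p be the true DLT rate at a level. Under Table 7 a level clears with 0/3, or with 1/3 followed by 0/3:

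E(p) = (1−p)³ + 3p(1−p)²·(1−p)³ = (1−p)³ + 3p(1−p)⁵

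| p | 10% | 20% | 30% | 40% | 50% | 60% |
|---|---|---|---|---|---|---|
| E(p) | 0.906 | 0.709 | 0.494 | 0.309 | 0.172 | 0.082 |
| Section 10.2 | 0.91 | 0.71 | 0.49 | 0.31 | 0.17 | 0.08 |

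All six agree. The patient totals also reproduce: 6 + 12 = 18 and 3 + 12 = 15.

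**2. Apply each text to the case where both levels clear.**

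| Text | Level 1 | Level 2 | Result |
|---|---|---|---|
| 10.2 | Fails: the next level shows fewer than one-third DLTs | Fails: there is no next level | No MTD |
| 3.1.2, first alternative | Met | Met | Either, unless the highest is understood |
| Table 7, escalation rows | Go to level 2 | Go to a level that does not exist | No row applies |
| Table 7, last row | Not triggered: no maximally administered dose has been declared | Not triggered | No dose named |

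**3. What the sizing implies.** Section 10.2 plans 6 to 9 further patients, to give 12 at the MTD. Section 2.3.2.1 says up to 9. Adding 9 means 12 − 9 = 3 patients were already at the MTD. If level 2 failed, Table 7 would first bring level 1 up to 6, leaving 12 − 6 = 6 to add. So 9 fits level 2 chosen after 0/3, which is a result that 10.2's definition excludes.

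**4. How often the case would arise.** The documents give no DLT rates for the combination, so p1 and p2 are assumed.

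- Both clear: E(p1)·E(p2), with E(0.05) = 0.973.
- 10.2 returns level 1: L(p1)·[1 − E(p2)]. Here L(p) = (1−p)⁶ + 6p(1−p)⁵ is the chance of at most 1/6, which includes Table 7's back-fill of level 1. L = 0.967, 0.886, 0.655 and 0.420 at 5%, 10%, 20% and 30%.
- Neither level tolerated: the remainder, including level 1 failing after back-fill.

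| Assumed p1 / p2 | Both clear (10.2 gives no MTD) | 10.2 returns level 1 | Neither tolerated |
|---|---|---|---|
| 5% / 10% | 0.973 × 0.906 = 0.88 | 0.09 | 0.03 |
| 10% / 20% | 0.906 × 0.709 = 0.64 | 0.26 | 0.10 |
| 20% / 30% | 0.709 × 0.494 = 0.35 | 0.33 | 0.32 |
| 30% / 40% | 0.494 × 0.309 = 0.15 | 0.29 | 0.56 |

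**The case against.** The strongest reply is that nobody would be misled. Section 3.1.2 is the operative escalation section, and its first alternative lets a tolerated level 2 be the MTD with nothing tested above it. The word maximum already points to the higher of two tolerated doses. The expansion sizing assumes that level 2 can be chosen, and the MTD will be written in by an amendment that, under the Statement of Compliance, needs IRB approval before it is implemented.

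Most of this stands, and it limits the point. A reader might infer more than the documents support in four ways:

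- **That the trial would have no primary result.** Only 10.2 gives none. Section 3.1.2 can name level 2, and the adverse-event endpoint is unaffected.
- **That Table 7 would send the expansion to level 1 after level 2 clears.** This takes the table's description of the maximally administered dose as the highest one given and applies it outside the rows where it appears. Such a dose is declared only when DLTs stop escalation. The last row also concerns the recommended phase 2 dose and is worded as a general rule.
- **That failure of level 1 is a second defect, because no lower dose exists.** In that case escalation stops and no level qualifies under 10.2, which is a sensible outcome. It only needs stating.
- **That 0.15 to 0.88 is a risk of choosing a wrong dose.** It is the chance that both levels clear, under assumed rates.

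The reply does not remove the conflict. Section 10.2 is the statistical definition of a primary endpoint, it gives the wrong answer for a tolerated top dose, and no text ranks it below 3.1.2.

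**Conclusion.** The point holds as an inconsistency between definitions, with 10.2 wrong as written for the top dose. That conclusion follows from the text and needs no assumption. Section 3.1.2 admits level 2 but leaves out that the highest tolerated level is meant, and Table 7 is silent once level 2 clears.

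The affected case is not remote. Its probability is about 0.88, 0.64, 0.35 or 0.15 across the four assumed pairs of DLT rates, using the escalation rule that reproduces the plan's table. It is the most likely outcome in the first three pairs and the least likely in the fourth.

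The documents do not show that a wrong dose would be given or that the sample size is wrong. The intended reading is recoverable, so the severity is that of a wording correction to a wrong rule, to be made before the DLT results are known.

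**What to change.** 1. In 10.2 and 3.1.2, use one definition: the MTD is the highest dose level studied at which 0/3 or at most 1/6 DLT-evaluable patients have a DLT in the first 28 days. Delete the next-higher-level condition from 10.2.
2. State that if level 2 meets this definition, it is the dose for Cohort 2 and is reported as the highest dose tested, with the MTD not exceeded.
3. State that if level 1 fails, no MTD is declared and Cohort 2 does not open.
4. Add a row to Table 7 for level 2 cleared (0/3, or 1/3 then 0/3): escalation ends and Cohort 2 opens at level 2.

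The cost is a wording amendment with IRB review. Escalation decisions, the level 1 back-fill, cohort sizes, the totals of 15 and 18 and the ceiling of 20 all stay as they are.

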2.3.2 Treatment Assignment and Randomization/Stratification Procedures

2.3.2.1 Cohorts

Number	Name	Description
1	Mature T-cell malignancies: Dose Escalation	Relapsed/refractory mycosis fungoides/Sézary syndrome, adult T-cell leukemia/lymphoma acute, chronic, and lymphoma subtype (up to 12 evaluable patients)
2	Mature T-cell malignancies: Dose Expansion	Relapsed/refractory mycosis fungoides/Sézary syndrome, adult T-cell leukemia/lymphoma acute, chronic, and lymphoma subtype (up to 9 additional evaluable patients, 12 total evaluable at the MTD)

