10.3 POPULATION FOR ANALYSIS

10.3.1 Evaluable for toxicity:

All patients will be evaluable for toxicity from the time of their first treatment with rhIL-15 and mogamulizumab.

Abbreviated Title: IL-15+Mogamulizumab

Version Date: 11/16/2020

10.3.2 Evaluable for objective response:

Only those patients who have measurable disease present at baseline, have received at least one cycle of therapy, and have had their disease re-evaluated will be considered evaluable for response. These patients will have their response classified according to the definitions stated above, Section **6.3.** (NOTE: Patients who exhibit objective disease progression prior to the end of Cycle 1 will also be considered evaluable for response. All patients who initiate treatment and receive at least one dose of study drug are considered evaluable for toxicity and will not be replaced.)

10.3.3 Evaluable Non-Target Disease Response:

Patients who have lesions present at baseline that are evaluable but do not meet the definitions of measurable disease, have received at least one cycle of therapy, and have had their disease re-evaluated will be considered evaluable for non-target disease. The response assessment is based on the presence, absence, or unequivocal progression of the lesions.

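### Sections 10.2 and 10.3.2 give opposite replacement rules for a treated patient who is not MTD-evaluable, and 10.2 states both an accrual ceiling of 20 and a maximum of 18 enrolled

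*Combined protocol and SAP*

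**What the plan says.** **Replacement.** Section 10.2 bases the MTD on DLTs in the first cycle. Of a subject with no DLT who does not complete that 28-day cycle, it says "he or she will not be evaluable for determination of the MTD and would be replaced in the dose level". Section 10.3.2, on evaluability for objective response, ends with a NOTE in parentheses. The NOTE says that all patients who start treatment and receive at least one dose are "considered evaluable for toxicity and will not be replaced".

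**Numbers.** The cohort table in Section 2.3.2.1 counts evaluable patients: "up to 12 evaluable patients" in escalation, and "up to 9 additional evaluable patients, 12 total evaluable at the MTD" in expansion. Section 10.2 gives a minimum of 15 evaluable and says that "a maximum of 18 evaluable patients will be enrolled" if both levels take 6 patients. It continues: "To account of unevaluable patients, accrual ceiling will be set at 20". The Précis repeats the ceiling of 20 and its purpose.

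**Time.** The next sentence of 10.2 reads "It is expected that the accrual can be completed in 18 months". The section closes with "A maximum of 18 patients will be enrolled over 18 months, at a rate of 1 patient per month".

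**The concern.** The MTD is a primary endpoint and is decided on 3 or 6 patients per level. The rule for who counts, and who is replaced, should therefore read one way. Take a patient who is dosed, has no DLT, and progresses and leaves before day 28. Section 10.2 replaces that patient in the dose level; the NOTE in 10.3.2 says that no treated patient is replaced. The escalation probabilities in 10.2 are for cohorts filled with 3 or 6 evaluable patients. If the NOTE were followed, a level could be judged on fewer, and those probabilities would not apply.

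The enrolment figures bear on the same question, because the ceiling of 20 is there to make replacement possible. The closing sentence of 10.2 limits enrolled patients, not evaluable patients, to 18. Taken literally, it removes the allowance stated in the paragraph before.

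**Working it through.** **1. The plan's own figures.**

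Probability of escalating at true DLT rate p, with full cohorts: (1−p)³ + 3p(1−p)² × (1−p)³.

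- p = 10%: 0.729 + 0.243 × 0.729 = 0.906 (stated 0.91)
- p = 50%: 0.125 + 0.375 × 0.125 = 0.172 (stated 0.17)
- p = 20%, 30%, 40%, 60%: 0.709, 0.494, 0.309, 0.082 (stated 0.71, 0.49, 0.31, 0.08)

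The whole table reproduces.

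Evaluable patients = number at the other level + 12 at the MTD. Maximum 6 + 12 = 18; minimum 3 + 12 = 15. Both match 10.2. This assumes full cohorts of 3 or 6. Table 7 stops escalation at 2 or more DLTs, so a level could close early. For example, 1 DLT in the first 3 and another in the fourth patient would give 4 + 12 = 16.

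**2. The two replacement rules, side by side.**

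| Patient | Section 10.2 | NOTE in 10.3.2 |
|---|---|---|
| Dosed, DLT in cycle 1 | Counts for the MTD | Not replaced |
| Dosed, no DLT, completes 28 days | Counts for the MTD | Not replaced |
| Dosed, no DLT, leaves before day 28 | Not MTD-evaluable, replaced | Not replaced |

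Only the third row conflicts, and it is the only group for which 10.2 has a replacement rule.

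**3. Places left for replacements.**

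- Ceiling of 20: 20 − 18 = 2 places if 18 evaluable are needed; 20 − 15 = 5 if 15 are needed.
- Closing sentence read as a cap of 18 enrolled: 18 − 18 = 0 and 18 − 15 = 3.

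**4. Accrual time at the stated rate.** 18 patients ÷ 1 per month = 18 months, which agrees with the closing sentence. 20 ÷ 1 = 20 months. Enrolling 20 in 18 months would need 20 ÷ 18 = 1.11 per month.

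**5. Illustration only.** The documents give no unevaluable rate, so u = 5%, 10% and 20% are assumptions, applied independently and equally to all patients. With q = 1 − u, the chance of at least 18 evaluable is P(Bin(20, q) ≥ 18) with 20 enrolled, and q¹⁸ with 18 enrolled.

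| Assumed u | 20 enrolled | 18 enrolled |
|---|---|---|
| 5% | 0.92 | 0.40 |
| 10% | 0.68 | 0.15 |
| 20% | 0.21 | 0.02 |

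The 20-enrolled column describes the ceiling that the plan already has. The 18-enrolled column applies only if the closing sentence is a true enrolment cap and only where 18 evaluable are needed. If 15 suffice, the corresponding chances are 1.00, 0.99 and 0.80 with 20 enrolled, and 0.99, 0.90 and 0.50 with 18.

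**The case against.** The best defence is that both problems are loose wording around a clear design. The NOTE sits under response evaluability and speaks of toxicity. It can be read as keeping every dosed patient in the toxicity set, while 10.2, which is specific to the MTD and the dose level, governs replacement. The Précis, Section 2.3.2.1 and Section 10.2 all count evaluable patients or allow for unevaluable ones. The closing sentence of 10.2 may simply have lost the word evaluable.

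Much of this stands. Section 10.2 is very probably the intended rule, and 20 the intended ceiling. But the NOTE covers all treated patients and does not state the narrower meaning. A lost word still leaves a wrong enrolment figure in the sample-size section.

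The defence also succeeds on accrual time. A reader might infer that the 18-month expectation is wrong. The documents do not show that, because 20 is a ceiling and not the expected number. At an assumed 10% unevaluable, 15 to 18 evaluable patients need 15 ÷ 0.9 = 16.7 to 18 ÷ 0.9 = 20 enrolled, and 18 months at 1 per month lies inside that range. What is missing is the time needed if the ceiling is reached.

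A reader might also infer a sample-size error or a defective escalation table. Neither is present: both reproduce.

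**Conclusion.** Two internal contradictions stand in the current text. First, a dosed patient with no DLT who leaves before day 28 is replaced under 10.2 and not replaced under the NOTE in 10.3.2. Second, 10.2 sets a ceiling of 20 and then a maximum of 18 enrolled; the difference is 2 patients, which is the whole replacement allowance when 18 evaluable are needed. At 1 per month the ceiling corresponds to 20 months, 2 more than the only duration given.

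These points follow from the text and simple arithmetic, and need no assumption. The probabilities of reaching 18 evaluable rest on assumed rates and, for the lower set, on a reading of the closing sentence that is probably not intended. They show why the enrolment figure matters and do not forecast a shortfall. The point should be fixed because it concerns who counts for a primary endpoint and a stated sample size, and because the repair is small.

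**What to change.** 1. **Section 10.3.2, NOTE.** Delete the no-replacement clause, or limit it to the toxicity population. Add that replacement for MTD evaluability follows 10.2 and that all treated patients stay in the safety set.
2. **Section 10.2, last sentence.** State a maximum of 20 enrolled, of whom up to 18 evaluable.
3. **Section 10.2, rate and duration.** Make them agree. One way is to keep 18 months as the expected accrual time and add that, at 1 patient per month, accrual takes up to 20 months if the ceiling is reached.

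The evaluable range, the ceiling of 20 and the escalation table do not change. The cost is a few sentences in two sections and a stated worst-case accrual about 2 months longer.
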